### **12.0 STATISTICAL CONSIDERATIONS**

This is a single arm, open label study designed to evaluate the safety and efficacy of idelalisib in IgM-associated AL amyloid patients. Patients will receive treatment until progression or unacceptable toxicity. Treatment will be comprised of idelalisib at 100 mg orally twice daily.

#### **12.1 Study Design/Endpoints**

The primary endpoint of the current study is:

- To assess the hematologic overall response rate (ORR) of idelalisib in IgM-associated AL amyloid patients.

The secondary endpoints are:

- To assess the safety and tolerability of idelalisib
- To evaluate organ response
- To evaluate progression free survival
- To measure impact of idelalisib treatment on quality of life

## 12.2 Sample Size/Accrual Rate

We assume a total of 6 patients per year for 4 years meeting inclusion/exclusion criteria, with approximately 60% enrollment for a total of 15 patients. Using an optimal 2-stage design, we assume  $\alpha=.05$ ,  $p_0 = .05$  and  $p_1 = .25$ , where  $p_0$  and  $p_1$  are the response probabilities under the null and alternative hypotheses, respectively. Then we would have 80% power to detect a statistically significant response rate with 9 patients enrolled in Stage 1, proceeding to 9 patients enrolled in Stage 2 only if at least one patient has a response during the first stage. Using this design the intervention would be declared successful if at least a total of 3 responses are observed during the study period.

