### 1.1.3 Patient population: (Specific inclusion and exclusion criteria are detailed in section 3)

### 1.1.4 Number of sites: 1, Boston Medical Center, [name]

### 1.1.5 Number of patients: 18 patients

### 1.1.6 Primary Objective:

- To determine the hematologic overall response rate (ORR) in IgM associated AL amyloidosis to a fixed dose of idelalisib. Response rates will categorized into complete response (CR), very good partial response (VGPR), partial response (PR) and progressive disease (PD) according to standard criteria (Gertz et al. 2010).

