### 2.1.8. Clinical Efficacy

Idelalisib has shown to be active and well tolerated in a range of B-cell malignancies (Benson 2013; Brown 2013). Idelalisib is highly active as monotherapy in CLL, FL, SLL, LPL, MZL and MCL. Responses to idelalisib are characterized by rapid and durable reductions in lymphadenopathy. Consistently positive results have been demonstrated on a number of endpoints including ORR, DOR and PFS. Idelalisib results thus far support its continued evaluation in subjects with B-cell malignancies. Most of the available clinical efficacy data is based on a dose of 150 mg PO twice daily.

Results from the 101-09 study were recently published (Gopal 2014). In this study, 125 patients with indolent NHL (including 10 patients with WM) who had not had a response to rituximab and an alkylating agent or had had a relapse within 6 months after receipt of those therapies received idelalisib at 150 mg PO BID until disease progression or withdrawal from study. The response rate was 57% with 6% CR rate. The median time to response and DOR were 2 months and 12.5 months, respectively, with a median PFS of 11 months. Based on this study, among the 10 WM patients, 1 PD, 1 SD, 6 MR and 2 PR were observed.

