#### 4.1.4 Duration of Participation

Participants will continue to take Idelalisib per-protocol until disease progression or unacceptable adverse event. Study visits will occur two weeks after starting Idelalisib, then monthly from the start of Idelalisib for three months, followed by every three months from the start of Idelalisib thereafter until disease progression or the start of another line of therapy, whichever occurs first. For patients who have responded but come off Idelalisib for reasons other than progression, they will be followed every 6 months until progression or another line of therapy. An end of study visit will take place 30 days following the last dose of Idelalisib. The duration for individuals, and duration of the study, are dependent upon disease response. We anticipate no more than 2 years duration for individual subjects. We anticipate the study will remain active for a total of 4 years including enrollment, treatment, follow-up and data analysis.

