#### 8.5 Progression-Free Survival

Progression-Free Survival (PFS) is defined as the duration of time from start of treatment to time of objective disease progression (including initiation of new therapy or death). Follow-up will continue until disease progression, which we anticipate to be no more than 2 years.

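### Section 12.2 forecasts 15 patients for a design that needs up to 18; that 9+9 design has exact type I error 0.053, and the optimal design for the stated inputs is 9+8 = 17

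*Combined protocol and SAP*

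**What the plan says.** Section 12.2 opens with an accrual forecast: 6 patients a year for 4 years meeting the entry criteria, "with approximately 60% enrollment for a total of 15 patients". It then sets the design. "Using an optimal 2-stage design, we assume" introduces alpha = .05, a null response rate of .05 and an alternative of .25, with a claimed power of 80%. Stage 1 has 9 patients, "proceeding to 9 patients enrolled in Stage 2 only if at least one patient has a response during the first stage". At the end, "the intervention would be declared successful if at least a total of 3 responses are observed during the study period". The maximum is therefore 9 + 9 = 18, which agrees with section 1.1.5 ("Number of patients: 18 patients").

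On timing, section 4.1.4 says: "We anticipate the study will remain active for a total of 4 years including enrollment, treatment, follow-up and data analysis". Section 8.5 says of progression-free survival (PFS): "Follow-up will continue until disease progression, which we anticipate to be no more than 2 years".

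**The concern.** Three things do not fit together.

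- **Forecast against design.** An accrual statement should show that the design can be completed. This one predicts three patients fewer than the design needs once stage 2 opens, and the plan does not say how the three-response threshold would apply to 15 patients.
- **Design against inputs.** An optimal two-stage design minimizes expected sample size under the null, subject to both error limits. The 9+9 rule breaks the type I error limit, so it cannot be the optimal design at alpha = .05.
- **Accrual against duration.** Section 12.2 uses 4 years for accrual alone. Section 4.1.4 allows 4 years for accrual, treatment, follow-up and analysis together.

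This is the only sample-size paragraph, and it governs the primary endpoint. What is at stake is the chance of missing an active drug if accrual stops at the forecast, and short PFS follow-up for patients who enroll late.

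**Working it through.** **Inputs (all from section 12.2).** p0 = .05, p1 = .25, alpha = .05, power 80%; stage 1 of 9, continue at 1 or more responses, success at 3 or more in total. Accrual is 6 a year × 4 years × about 60%.

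**Formula.** For total size n, with X₁ the number of stage 1 responses:

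P(success) = P(X₁ ≥ 3) + P(X₁ = 1)·P(Bin(n−9, p) ≥ 2) + P(X₁ = 2)·P(Bin(n−9, p) ≥ 1)

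**The plan's own design, 9+9.**

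- At p = .05: 0.0084 + 0.2985 × 0.0712 + 0.0629 × 0.3698 = 0.0529. This is the type I error. The stated limit is .05.
- At p = .25: 0.3993 + 0.2253 × 0.6997 + 0.3003 × 0.9249 = 0.835. This is the power. The stated figure is 80%, so power is met with margin.

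**Same rule at other totals.**

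| Design | Type I error (p = .05) | Power (p = .25) |
|---|---|---|
| 9+6 = 15 | 0.0348 | 75.1% |
| 9+7 = 16 | 0.0406 | 78.5% |
| 9+8 = 17 | 0.0466 | 81.2% |
| 9+9 = 18 | 0.0529 | 83.5% |

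**Which design is optimal.** I searched all two-stage designs up to 40 patients with type I error ≤ .05 and power ≥ .80.

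- Smallest expected size under p0: 9+8 = 17, continue at 1 or more, success at 3 or more. Expected size is 9 + 8 × 0.3698 = 11.96, against 9 + 9 × 0.3698 = 12.33 for 9+9.
- Smallest maximum (minimax): 12+4 = 16, continue at 1 or more, success at 3 or more. Type I error is 0.0427, power 80.1%, expected size under p0 13.84.

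Other readings of alpha do not give 9+9. A limit of .025 gives 8+15 = 23, and a limit of .055 or .06 gives 7+12 = 19.

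**How often stage 2 opens.** P(0 of 9) is 0.95⁹ = 0.6302 at p0 and 0.75⁹ = 0.0751 at p1, so stage 2 opens with probability 37.0% and 92.5% respectively. Expected enrollment under 9+9 is 12.3 at p0 and 9 + 9 × 0.9249 = 17.3 at p1. The forecast of 15 therefore falls short mainly when the drug works.

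**Accrual.** 6 × 4 × 0.60 = 14.4, stated as 15. Exactly 15 needs 15/24 = 62.5%, or 3.75 a year.

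| Total | Years at 3.6 a year | Years at 3.75 a year | Enrollment share needed within 4 years |
|---|---|---|---|
| 16 | 4.4 | 4.3 | 67% |
| 17 | 4.7 | 4.5 | 71% |
| 18 | 5.0 | 4.8 | 75% |

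**Follow-up if the study closed at year 4.** This assumes even accrual over all 4 years and a firm closing date; the plan states neither. At 3.6 to 3.75 a year, about 4 of 15 patients would have under 1 year of follow-up (3.6 to 3.75), about 7 under 2 years (7.2 to 7.5), and about 1 under 3 months (0.9).

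**The case against.** The strongest reply is that the design size is not contradictory. Sections 1.1.5 and 12.2 both give 18. The 15 is a forecast in approximate terms, no text closes enrollment there, and 18 is only a maximum. Under the null, 9 patients suffice 63% of the time. This stands, and it makes the 75% power figure conditional on an event the plan does not schedule. It does not explain why the forecast cannot fill the design.

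On type I error, the excess is 0.003, 0.0529 rounds to .05, and power exceeds its target. The size of the excess is indeed small. Rounding does not rescue the optimal label, though, since relaxing the limit to .055 gives 7+12.

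A third point is that 17 has less slack than 18: a stage 2 patient who cannot show a response leaves 9+7 and 78.5% power. That arithmetic is right. But section 12.2 does not present the eighteenth patient as an allowance. Section 12.4 keeps all eligible enrolled participants in the main analysis, so p1 = .25 already has to be read as a rate among all of them.

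On timing, the 4 years and the 2 years are expectations, and section 8.5 follows patients to progression. The late-enrollee counts therefore hold only under the closing-date assumption. Hematologic response is probably little affected. Section 2.1.8 reports of the indolent NHL study: "The median time to response and DOR were 2 months and 12.5 months, respectively, with a median PFS of 11 months". That study used 150 mg twice daily in a different disease, so this reassurance is borrowed.

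**Conclusion.** The concern holds. As written, section 12.2 forecasts 15 patients (14.4 by its own inputs) for a design needing up to 18. That design exceeds the stated alpha (0.053 against .05) and is not the optimal one for its inputs (9+8 = 17).

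The type I error excess alone is minor; the accrual gap carries more weight. If stage 2 opened and accrual ended at 15 under the same threshold, a drug with a true 25% response rate would be declared a failure about 25% of the time (1 − 0.751), against 16.5% at 18. So the stated alpha fails at 18, and the stated power would fail at 15.

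The design figures are exact binomial results and need only the plan's inputs. The timeline figures rest on the plan's accrual rate. On that rate, 4 years of accrual uses up the whole duration in section 4.1.4, mainly at the expense of PFS follow-up. The plan should be corrected; the correction is small.

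**What to change.** **Design.** In sections 12.2 and 1.1.5, state 9+8 = 17: continue if at least 1 of 9 responds, success at 3 or more in total, exact type I error 0.047, power 81%.

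**Accrual and duration.** Replace the 15-patient forecast with about 4.7 years of accrual to 17 at 3.6 a year, or justify the 71% enrollment share that reaches 17 in 4 years. Revise the total in section 4.1.4 to match, and state there how much of it is enrollment and how much is follow-up after the last patient enters. Moving from 18 to 17 does not close the accrual gap by itself, so both edits are needed.

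**Cost.** Stage 1, the continuation rule and the success threshold stay as they are. The maximum falls by one patient and power falls from 83.5% to 81.2%, still above 80%. The study runs longer than 4 years; even with the higher enrollment share, accrual alone fills 4 years.

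**Alternatives.**

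- 12+4 = 16 also meets both targets (0.043, 80.1%, about 4.4 years of accrual). It enlarges stage 1, has almost no power margin, and is minimax, not optimal (expected size under p0 13.8 against 12.0).
- If 18 is kept, section 12.2 should report type I error 0.053 and power 83.5% and drop the optimal label. The accrual forecast still needs correcting.
- If the sponsor expects to stop at 15, the plan should say so as a design change, with power about 75% and type I error 0.035.

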## 11.0 REGULATORY CONSIDERATIONS

### 11.1 Protocol Amendments

Any amendment to this protocol must be agreed to by the Principal Investigator and reviewed and approved by Gilead. Amendments should only be submitted to IRB/EC after consideration of Gilead review. Written verification of IRB approval will be obtained before any amendment is implemented.

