## 12.4 Reporting and Exclusions

All participants who met the eligibility criteria and were enrolled in the trial will be included in the main analysis of the response rate. All conclusions will be based on all eligible participants.

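### The 9+9 two-stage rule has an exact type I error of 0.053 and is not the optimal design for the stated inputs, which is 9+8 = 17 (minor correction)

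*Combined protocol and SAP*

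**What the plan says.** Section 12.2 (Sample Size/Accrual Rate) names the method, "Using an optimal 2-stage design, we assume", and sets alpha at .05, the null response rate p0 at .05 and the alternative p1 at .25. The power claim reads: "Then we would have 80% power to detect a statistically significant response rate". For the stage sizes and the continuation rule, the section has "with 9 patients enrolled in Stage 1, proceeding to 9 patients enrolled in Stage 2 only if at least one patient has a response". The final rule is that "the intervention would be declared successful if at least a total of 3 responses are observed during the study period". Section 1.1.5 gives the matching total, "Number of patients: 18 patients".

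The plan reports no exact type I error, expected sample size or reason for a second stage of 9. Section 12.2 also forecasts accrual at 6 patients a year for 4 years, "with approximately 60% enrollment for a total of 15 patients". Section 12.4 defines the analysis set: "All participants who met the eligibility criteria and were enrolled in the trial will be included in the main analysis of the response rate".

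**The concern.** An optimal two-stage design is the one with the smallest expected sample size under the null among all designs that keep the type I error at or below alpha and the power at or above target. The plan gives every input needed to check whether 9+9 is that design, and it is not. Its type I error is slightly above the limit.

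This is the only formal decision rule for the primary endpoint. A report that repeats section 12.2 would claim an alpha and a design label that the rule does not have, and any reader can recompute both. The stage 1 rule, the success threshold and the 80% power claim are not at fault at 18 patients.

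**Working it through.** **Inputs (all from section 12.2).** p0 = 0.05, p1 = 0.25, alpha = 0.05, power = 0.80; n1 = 9, n2 = 9; continue if stage 1 has at least 1 response; success at 3 or more in total.

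**Formula.** Let b(x; n, p) be the binomial probability of x responses in n patients and X2 the number of stage 2 responses. Then

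P(success) = b(1; 9, p) × P(X2 ≥ 2) + b(2; 9, p) × P(X2 ≥ 1) + P(X1 ≥ 3).

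**The plan's design, n2 = 9.**

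- p = 0.05: 0.29854 × 0.07121 + 0.06285 × 0.36975 + 0.00836 = 0.02126 + 0.02324 + 0.00836 = **0.05286**.
- p = 0.25: 0.22525 × 0.69966 + 0.30034 × 0.92492 + 0.39932 = 0.15760 + 0.27779 + 0.39932 = **0.83471**.
- Probability of stopping after stage 1 under p0: 0.95^9 = 0.6302. Expected N under p0: 9 + 0.3698 × 9 = **12.33**.

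The stated 80% power is met. The type I error exceeds 0.05 by 0.29 percentage points. The rule would attain exactly 0.05 at a null rate of 0.0489.

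**One patient fewer, n2 = 8.**

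- p = 0.05: 0.29854 × 0.05724 + 0.06285 × 0.33658 + 0.00836 = **0.04660**.
- p = 0.25: 0.22525 × 0.63292 + 0.30034 × 0.89989 + 0.39932 = **0.81216**.
- Expected N under p0: 9 + 0.3698 × 8 = **11.96**.

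**Search.** Over total sizes up to 44, requiring type I error ≤ 0.05 and power ≥ 0.80, the smallest expected N under p0 belongs to 9+8 = 17 with these cut-offs. The next is 6+23 = 29, at 12.09. No design with 9 in stage 1 and 18 in total qualifies.

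| Design | Continue / success | Type I error | Power | Expected N under p0 |
|---|---|---|---|---|
| 9+9 = 18 (plan) | ≥1 / ≥3 | 0.0529 | 0.835 | 12.33 |
| 9+8 = 17 (optimal) | ≥1 / ≥3 | 0.0466 | 0.812 | 11.96 |
| 9+9 = 18 | ≥1 / ≥4 | 0.0105 | 0.682 | 12.33 |
| 9+6 = 15 | ≥1 / ≥3 | 0.0348 | 0.751 | 11.22 |

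**Does a looser alpha rescue the label?** No. With the limit relaxed to 0.053, which admits 9+9, the optimum becomes 7+12 = 19 (type I error 0.0529, power 0.807, expected N 10.62). 8+10 = 18 (0.0505, 0.817, 11.37) and 9+8 also have a smaller expected N than 9+9.

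**How often the decision changes.** 9+9 and 9+8 differ only when patient 18 supplies the third response: b(1; 9, p) × b(1; 8, p) × p + b(2; 9, p) × b(0; 8, p) × p.

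- p = 0.05: 0.00417 + 0.00208 = 0.00625.
- p = 0.25: 0.01503 + 0.00752 = 0.02255.

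To rounding, these equal the differences in type I error and power between the two designs.

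Suppose the trial continues and ends with exactly 3 of 18. There are C(9,1)C(9,2) + C(9,2)C(9,1) + C(9,3) = 324 + 324 + 84 = 732 equally likely arrangements. In C(9,1)C(8,1) + C(9,2) = 72 + 36 = 108 of them (14.8%), patient 18 is the third responder. In the other 85%, 9+8 would also declare success.

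**The case against.** The best case for leaving the text alone has four parts.

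- **Rounding.** The plan gives alpha to two decimals and never calls it a ceiling, and 0.0529 rounds to .05. That is a fair reading of the alpha statement taken alone. It does not save the word optimal, because 9+9 is beaten under the looser limit too.
- **Accrual.** The excess arises only if 18 eligible patients are analysed. One ineligible patient in Stage 2 leaves 9+8 (0.047), and the plan's own forecast of 15 gives 0.035. This stands as a limit on the size of the problem. It does not correct the stated design, and the same shortfall takes power to 0.75, below the 80% claimed.
- **An allowance for losses.** The 18th patient might be a margin added to 17. The documents do not say so. Section 12.2 makes all 18 part of the design, and section 12.4 counts every eligible enrolled patient toward the success rule.
- **Proportion.** Going to 17 gives up 2.3 points of power to remove 0.6 points of type I error. This is a good argument for correcting the wording rather than the sample size. A total of 18 is also compatible with alpha ≤ 0.05: 12+6, continuing at 2 or more with success at 3 or more, gives 0.0457 and 0.8003, with expected N 12.71. That changes stage 1 and is not optimal either.

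**Conclusion.** The point holds as a minor correction. At 18 eligible patients the stated rule has type I error 0.0529 and power 0.835, and the optimal design for the stated inputs is 9+8 = 17 (0.0466 and 0.812). The wrong label does not depend on how .05 is read. The alpha part depends on treating .05 as an upper limit, which is the usual convention for these designs.

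The calculation assumes independent patients with a common response probability, and analysis of exactly the planned number in each stage. A result of 3 of 18 would not in general be in doubt.

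**What to change.** Choose one.

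**Option B (less disruptive, and sufficient).** Keep 9+9 and 18. In section 12.2 state the attained type I error of 0.053 and power of 0.83, and delete the word optimal. That is three edits, with no change to sample size or decision rule. The cost is an openly stated type I error slightly above 0.05.

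**Option A (if 0.05 must be a strict limit).** Set Stage 2 to 8 and the total in section 1.1.5 to 17. State the attained type I error of 0.047 and power of 0.81, and add a sentence closing enrollment at the 17th eligible patient, since section 12.4 would otherwise bring an 18th into the analysis. That is five edits, and the label optimal is then correct. The cost is power of 0.81 instead of 0.835.

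Do not raise the threshold to 4 of 18: power falls to 0.68.

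Under either option, add one sentence to section 12.2 saying that the stated power assumes full accrual. The projection there is 15 patients (6 × 4 × 0.60 = 14.4), and 9+6 with the same cut-offs has power of only 0.75.

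Either option is a protocol amendment. Section 11.1 requires the drug supplier's review and approval, and "Written verification of IRB approval will be obtained before any amendment is implemented". The correction can travel with another amendment.

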## 12.3 Stratification Factors

No stratification factors will be applied to any analysis.

## 12.4 Reporting and Exclusions

All participants who met the eligibility criteria and were enrolled in the trial will be included in the main analysis of the response rate. All conclusions will be based on all eligible participants.

## 14.0 APPENDICES

### 14.1 APPENDIX A: Performance Status Criteria

ECOG Performance Status Scale		Karnofsky Performance Scale	
Grade	Description	Percent	Description
0	Normal activity. Fully active, able to carry on all pre-disease performance without restriction.	100	Normal, no complaints, no evidence of disease.
		90	Able to carry on normal activity; minor signs or symptoms of disease.
1	Symptoms, but ambulatory. Restricted in physically strenuous activity, but ambulatory and able to carry out work of a light or sedentary nature (e.g., light housework, office work).	80	Normal activity with effort; some signs or symptoms of disease.
		70	Cares for self, unable to carry on normal activity or to do active work.
2	In bed < 50% of the time. Ambulatory and capable of all self-care, but unable to carry out any work activities. Up and about more than 50% of waking hours.	60	Requires occasional assistance, but is able to care for most of his/her needs.
		50	Requires considerable assistance and frequent medical care.
3	In bed >50% of the time. Capable of only limited self-care, confined to bed or chair more than 50% of waking hours.	40	Disabled, requires special care and assistance.
		30	Severely disabled, hospitalization indicated. Death not imminent.
4	100% bedridden. Completely disabled. Cannot carry on any self-care. Totally confined to bed or chair.	20	Very sick, hospitalization indicated. Death not imminent.
		10	Moribund, fatal processes progressing rapidly.
5	Dead.	0	Dead.

14.2

**Mission:**

The Cancer Center Data Safety Monitoring Committee (DSMC) functions to ensure the safety of participants in investigator-initiated, interventional clinical trials conducted by BUMC Cancer Center members by monitoring clinical trial progress and the collection, validity and integrity of the data collected on clinical trials under its jurisdiction. The committee ensures compliance with FDA, NCI and IRB requirements. The policies and procedures of the Data and Safety Monitoring Committee follow NCI guidelines.

